12.1. Compliance

The sponsor, the investigators and the CRO undertake to carry out this trial in accordance with the protocol and the ethical, legal and regulatory provisions in force: the principles of the "Helsinki Declaration", national legislation and regulations relating to clinical trials in France and Belgium (Jardé Law and its implementing decrees, Belgian law of 7 May 2004 on human experimentation and Royal Decree 1999-03-18/34 relating to medical devices) and in accordance with regulations relating to medical devices (Regulation (EU) 2017/745 on medical devices, Standard EN ISO 14155:2011 relating to the clinical investigation of medical devices for human subjects — Good clinical practice).

The Clinical Investigation Protocol is drawn up in accordance with Annex A of Standard EN ISO 14155:2011.

12.2. Obligations before starting the trial:

Ethics Committees

In France:

The CRO undertakes to submit the protocol to a Committee for the Protection of Individuals on behalf of the sponsor, designated by drawing lots, to seek its prior opinion, in accordance with the procedures defined by Article 24-II of Decree no. 2016-1537 of 16 November 2016. The information provided concerns the nature of the trial and the safeguards provided for patients taking part in this clinical trial.

In Belgium:

The CRO undertakes to submit the protocol to the Cliniques Universitaires Saint-Luc Hospital-Faculty Ethics Committee (CEHF) on behalf of the sponsor to seek its prior opinion, in accordance with the regulations in force (Belgian Law of 7 May 2004 on human experimentation and Article 2N10.2 of the Royal Decree 1999-03-18/34 relating to medical devices).

The trial will not be initiated in the investigating centers until a favorable opinion has been obtained from the relevant ethics committee in each country.

Competent authorities

As the study is category 1 research involving humans, the CRO undertakes to submit an application for clinical trial authorization on behalf of the sponsor to the competent authority in each country where the trial is taking place: the ANSM in France and the AFMPS in Belgium.

The procedures in France are carried out as part of the Pilot Phase for clinical trials (phase prior to the application of EU Regulation no. 2017/745) proposed by ANSM and the CPPs(Practical information guide for applicants 2019).

Personal data protection authorities (CNIL and APD)

This trial complies with the French law on information technology, files and freedoms (law no. 78-17 of 6 January 1978 amended by law no. 2018-493 of 20 June 2018 on the protection of personal data, and the General Data Protection Regulation (RGPD— Regulation (EU) 2016/679 of 27 April 2016). This trial meets the requirements of the MR001 reference methodology for consent-based research (Annexe 4).

This trial complies with the Belgian law of 8 December 1992 on the protection of privacy with regard to the processing of personal data, the specific rules of chapter 2 of the Royal Decree of 13 February 2001.

Financing & insurance

The sponsor, Septodont, is financing the clinical study.

Septodont has taken out a Sponsor Civil Liability policy for research with the insurance company HDI-Global SE in France and Belgium on 8 and 9 July 2020, in accordance with French and Belgian legal and regulatory provisions on research involving the human person and in particular the provisions of Law 88.1138 of 20/12/1988, amended by subsequent texts, in particular Law no. 2012-300 of 5 March 2012 and its implementing decree no. 2016-1537 of 16 November 2016 and Article 29 of the Belgian Law of 7 May 2004. The twoinitial insurance certificates are available at Annexe 5.

Subject allowances

No compensation is provided for participation in this study.

12.3. Obligations after the start of the trial:

From the first enrolment, the CRO on behalf of the sponsor will inform the competent authority and the CPP without delay of the effective start date of the investigation (Effective start date = signature of the consent form by the first person to take part in the trial).

The date of completion of the clinical trial will be sent by the CRO on behalf of the sponsor to the ANSM and the CPP within 90 days. The end date of the trial corresponds to the end of the follow-up of the last person followed as part of the protocol (date of receipt of the last 6-month follow-up questionnaire).

12.4. Archiving

All correspondence relating to the clinical study, regulatory authorizations, source documents and data collection documents must be filed and kept by the Sponsor and the investigators at each center for 15 years, in accordance with current regulations. The CRO will keep the data collection documents for a limited period after the end of the study (until the results are published).

12.5. Inspection / Audit

As part of this study, an inspection or audit may be carried out, as defined by the rules of Good Clinical Practice. Inspectors are entitled to check the documents, logistics, records and any other resources that the authorities consider to be associated with the clinical study and which may be located at the research site itself, at the sponsor's premises or at other establishments deemed relevant.

13. Process for obtaining informed consent

The investigator undertakes to inform the patient, orally and in writing, in a clear and fair manner, of the terms and conditions of participation in the OPTIFILL protocol; in particular, he/she will provide the patient with an information note.

The information given by the investigator to the patient will concern:

- the objectives, methodology and duration of the research,
- presentation of the system under investigation,
- the expected benefits, inconveniences and risks of the trial,
- the opinion of a CPP and authorization from the competent authority (ANSM or AFPMS),
- a ban on taking part in other trials at the same time.

Patients should also know:

- that they may refuse to take part in the trial,
- that they may withdraw their consent at any time for any reason,
- that they will not incur any additional financial burden as a result of their participation in the trial,
- that he/she must not participate simultaneously in another research project for one month following the end of the current research project,
- that they have rights of access, rectification, opposition and limitation of processing with regard to their personal data, in accordance with the General Data Protection Regulation (EU) 2016/679 of 27 April 2016).

The investigator must answer any additional questions that the patient may have about the study at the time of selection and throughout the duration of the research.

Prior to enrolment in the study, the subject's informed, free and express consent will be obtained in writing. The consent form will be signed and dated by the patient and the investigator. Participation in the OPTIFILL protocol will be specified in the patient's medical record; a copy of the consent form will be given to the patient, another will be kept by the sponsor in a sealed envelope, and the original will be kept by the investigator.

14. Adverse events, device-related adverse events and device defects

General provisions:

As part of this clinical trial, it is the investigator's responsibility to report all device defects and adverse events in the CRF on the pages reserved for this purpose (reporting process detailed in the following sections).

Tolerance monitoring begins as soon as the patient's consent is obtained and will continue until the end of the patient's participation in the protocol. Adverse events will beactively sought on the basis of patient declarations (follow-up logbook) and during clinical examinations and interviews carried out by the investigating team at each follow-up visit and until the end of the study.

The investigator will be on call during office opening hours so that patients can inform the investigator of any adverse events.

If the adverse event leads to the subject's participation being terminated, the "End of Clinical Investigation Form" at the end of the CRF will be completed by the investigator.

14.1. Definitions

The definitions below are in line with EN ISO 14155:2011 and Regulation (EU) 2017/745 on medical devices (including guide MDCG 2020-10/1) and current national regulations:

Device failure

Any defect in the identity, quality, durability, reliability, safety or performance of a device under investigation, including any malfunction, any error in use, or any defect in the information provided by the manufacturer.

Adverse event (AE)

Any adverse clinical event, unintended illness or injury, or any untoward clinical sign (including an abnormal laboratory finding) in participants, users or others, in the course of a clinical investigation, whether or not related to the device under clinical investigation.

- NOTE 1: This definition includes events related to the medical device under investigation or to the comparator.
- NOTE 2: This definition includes events linked to the procedures involved.
- NOTE 3: For users or other persons, the definition concerns only events linked to devices under investigation and comparator.

Adverse device effect (ADE)

Adverse event linked to the use of medical devices under investigation and comparator.

NOTE 1: This definition includes any adverse event resulting from insufficiencies or inadequacies in the instructions for use, deployment, implantation, installation and operation, or any malfunction of the medical device.

NOTE 2: This definition includes any event resulting from an error of use or intentional improper use of the medical device.

Serious adverse event (SAE)

Any adverse event leading to:

- a) death;
- b) a serious deterioration in the participant's state of health:
 - i) a life-threatening illness or injury;
 - ii) a permanent impairment of an anatomical structure or function;
 - iii) hospitalization or prolongation of the patient's hospitalization;
 - iv) medical or surgical intervention to prevent any life-threatening illness or injury or any permanent impairment of an anatomical structure or function;
 - v) a chronic illness;
- c) fetal distress, fetal death, congenital physical or mental impairment or congenital malformation;

NOTE: A planned hospitalization due to a pre-existing condition or a procedure required by the clinical investigation plan, without any serious deterioration in health, is not considered to be an SAE.

Serious adverse device effect (SADE)

Adverse effect of the device leading to one of the consequences characteristic of a serious adverse event (see previous definition).

Anticipated adverse device effect (A-ADE)

An anticipated adverse effect is one whose nature, incidence, severity and consequences have been identified in the current version of the risk analysis report or in the device's instructions for use.

Unanticipated adverse device effect (U-ADE)

An unanticipated adverse effect is an effect of the device, the nature, incidence, severity and consequences of which have not been identified in the previous version of the risk analysis report or in the instructions for use for the device.

New fact (Jardé Law) / Urgent safety measure (EU Regulation 2017/745)

A new fact is any new information that may lead to a reassessment of the benefits and risks of the research, to changes in the conduct of the trial or in the documents relating to the research, or to the suspension, interruption or modification of the research protocol. For the purposes of this trial, any serious adverse effect to the device will be considered a new fact.

An urgent safety measure, as defined in Article 2-paragraph 66 of EU Regulation 2017/745 on medical devices, is an event that is likely to result in an imminent risk of death, serious deterioration of health status or serious illness that may require prompt corrective action, and that is likely to result in significant morbidity or mortality in humans or that is unusual or unexpected in the place and time considered.

The sponsor will immediately inform the competent authorities and ethics committees of any new developments or urgent safety measures.

14.2. Process and time-frame for reporting an adverse event (including the date of the event, treatment, resolution, assessment of the seriousness and assessment of the relationship with the device under investigation).

14.2.1. Recording an adverse event

All AEs, whether or not related to the medical device under investigation or comparator, or to the endodontic treatment procedures, reported by the patient or observed by the investigator must be reported in the eCRF, specifying 1) the nature (clinical signs, symptoms, diagnoses), 2) the date and time of onset, 3) the duration, 4) end date and time, 5) the severity, 6) the therapeutic consequences, the ensuing evolution, and 7) relationship with the DM under investigation or the comparator DM or the endodontic treatment procedures (according to the investigator's opinion).

Clinical signs, symptoms and diagnoses should be described by the investigator/reporter using precise terminology, avoiding ambiguity and abbreviations; the location of symptoms may be specified if relevant. Based on this information, the CRO will code each AE using the IMDRF dictionary – appendices E and F (IMDRF, 2020).

Further instructions on how to register an AE can be found in the eCRF user guide provided by the CRO.

Health conditions related to the dental pathology studied which change during the clinical trial, and which are attributable to a lack of effectiveness of the medical device (e.g. failure of the endodontic treatment), are NOT considered as AEs and should therefore not be recorded as such.

Previous or ongoing medical conditions known at study entry should NOT be considered as AEs unless worsening has occurred. In this case, if a deterioration or exacerbation of an intercurrent condition previously reported in the patient's medical history occurs, the AE must be described using appropriate terminology (e.g. deterioration, exacerbation, etc.).

In the case of surgery or diagnosis, the cause leading to such a procedure is considered to be the AE rather than the procedure itself. In the case of death, the cause of death is considered to be the AE and the death its consequence.

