Description of the pain experienced by the patient in the 7 days post-operation.	Preoperative pain (VAS 0-100 mm), Post-operative pain at different times after root canal obturation, Maximum post-operative pain felt between T0 and 7 days, Time to onset of maximum pain	Preoperative (at the start of each endodontic treatment session, i.e. 1 or 2 sessions for root canal preparation and obturation), TO (end of endodontic treatment), T12h (or before going to bed or getting up the next day depending on the time at TO), T24h, T48h, T72h and 7 days (patient, investigator)

	T =	T , , , , , , , , , , , , , , , , , ,
Description of the use of oral painkillers in the 7 days following	Classes of painkillers,	T0 to D7 (patient, investigator)
surgery	Reason for use,	
	Frequency of painkiller intake,	
	Cumulative dose over 7 days	
	Proportion of patients who used an oral painkiller between T0 and D7	
Evaluation of adverse events following endodontic treatment	Proportion of patients with at least 1 AE	Continuously from T0 to 24 months for the BioRoot™ RCS
	Number of AEs;	arm, and 5 years for the PA1704 arm(investigator)
	Type of AE, intensity, level of attribution to the filling material or surgical technique.	
	Number of additional dental consultations for complications or significant postoperative pain.	
	Number of faults and description.	
Description of the surgical technique for first-line endodontic treatment (ET) or repeat endodontic treatment (RET) and any perioperative complications,	Type of anesthesia,	T0 (investigator)
	Technique for removing the old filling material (ER only),	
	Type of endodontic instruments used to shape the canal,	
	Type of disinfectant and rinsing solutions used and solution activation technique used,	
	Gutta-percha condensation technique,	
	Coronal restoration technique,	
	Description of any intra-operative complications.	
Evaluation of operator comfort and satisfaction with the use of the material	Comfort, practicality of handling the device, ease of applying the material, difficulties encountered, time, reproducibility of root canal preparation and obturation,	TO (CRF— investigator) then at the end of the trial (overall satisfaction questionnaire — investigator)
	Advantages and disadvantages of the ready-to-use form compared with the powder-liquid form.	
	Overall practitioner satisfaction.	

Table 3: List of secondary outcome measures.

✓ Methods and times for evaluating, recording and analyzing variables.

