14.2.4. Type and duration of follow-up of subjects after an AE

AEs will be followed by the Investigator until they are resolved (i.e. the event is resolved or the pathology is unlikely to change or the subject is lost to follow-up). All clinical and biological examinations deemed necessary by the investigator will continue until the patient returns to normal. The investigator will provide the sponsor with copies of all examination results and treatments related to the follow-up of events.

14.2.5. Reporting of serious adverse events (SAEs) to the sponsor:

As part of this category 1 research involving human beings, the investigator is obliged to notify the sponsor immediately, and for no more than 3 calendar days, of any serious adverse event occurring during the study in an included patient (MDCG 2020-10/1). The people who should be contacted are listed in the 14.5 section.

1/ Initial declaration:

This initial report should be made on a paper form entitled "Initial report of a serious adverse event" (blank form kept in the Trial Master File of the investigating site), indicating the date of occurrence, the severity, the relationship with the device under investigation or comparator (or the protocol) and the follow-up. The narrative report must be completed and sent to the CRO and the sponsor as soon as any new relevant information is obtained. Depending on the nature and seriousness of the event, anonymized copies of the patient's source documents may be attached. The information to be collected on the paper form for the initial notification of an SAE is as follows:

- Clear identification of the Investigator/Rapporteur with all contact details,
- Detailed identification of the subject (patient identifier in the study, site number, patient age at the start of the SAE, sex),
- Subject treatment group (device under investigation or comparator),
- Date of endodontic treatment (start date of treatment and date of root canal filling if different from start date),
- Description of the event (free text): nature of the symptoms observed, duration and severity of
 the symptoms, date of onset of the first signs of the AE (before it becomes an SAE), patient
 history and current treatments,
- The reason why this event is considered serious,
- The Investigator's opinion on the imputability of the medical device under investigation or the comparator or the investigation protocol (unrelated, possible, probable, certain),
- Corrective action and treatment.

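### Section 14.2.1 excludes failure-related changes in the treated tooth from AE recording with no exception for serious events, so an event that is serious under section 14.1 can miss the AE counts and the 3-day report.

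*Combined protocol and SAP*

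**What the plan says.** Section 14.1 defines an AE broadly: "Any adverse clinical event, unintended illness or injury, or any untoward clinical sign", arising "in the course of a clinical investigation, whether or not related to the device under clinical investigation". Lack of effectiveness is not excepted. An SAE is then an AE with one of the listed outcomes. These include hospitalisation, permanent impairment of a structure or function, chronic illness, and "medical or surgical intervention to prevent any life-threatening illness or injury or any permanent impairment of an anatomical structure or function".

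Section 14.2.1 narrows what is recorded. Its rule concerns "Health conditions related to the dental pathology studied which change during the clinical trial". A second limit is the cause: the rule reaches only those changes "which are attributable to a lack of effectiveness of the medical device (e.g. failure of the endodontic treatment"). When both limits are met, the change is not "considered as AEs and should therefore not be recorded as such". Its next paragraph deals with conditions already known at entry: they are not AEs unless they worsen, in which case they are.

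Section 14.2.5 requires the investigator to notify the sponsor immediately, and within 3 calendar days at most, "of any serious adverse event occurring during the study in an included patient". Section 7.7.6 compares the arms on AEs and on patients with at least one AE, and separately on patients who needed an extra dental consultation for a complication or pain. Table 3 in section 6.1 lists the latter as "Number of additional dental consultations for complications or significant postoperative pain".

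**The concern.** The two sections give different answers for the same event. Under 14.1, an acute problem in the treated tooth that puts the patient in hospital is an SAE. Under 14.2.1, if it is put down to failure of the endodontic treatment, it is not an AE at all.

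Section 3.3 describes the trial as the first use of PA1704 in humans. Sections 4.2 and 14.4 say that the device's adverse effects are not known, and section 14.6 provides no data monitoring committee. Expedited reporting by investigators is therefore a main safety channel, and the exclusion can close it. Investigators record AEs and know the arm (section 6.1), and no blinded assessor is assigned to decide between failure and AE. The rule could be applied differently by arm, and a material that failed more often would also have more events eligible for exclusion.

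**Working it through.** **Step 1. The chain of definitions.**
- 14.1: an SAE must first be an AE.
- 14.2.1: a change in the studied dental condition attributed to lack of effectiveness is not an AE.
- Hence such a change cannot be an SAE, whatever its outcome.
- 14.2.5 applies to SAEs only, so the 3-day report is not triggered. The duty in the same section to report SAEs within 30 days of the last visit falls away for the same reason, and so does the AE follow-up in 14.2.4.
- No passage in section 14 restores the route for serious events.

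**Step 2. Exit from the trial.** Sections 6.3 and 6.5.2 make failure with retreatment a reason to leave early. For a failure judged an emergency at 6 or 12 months, section 6.5.2 says that performance and safety evaluations stop at that point. Section 6.3 lists an SAE and treatment failure as separate exit reasons and gives no rule for an event that is both.

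**Step 3. Two opposing rules for lesion growth.** Periapical diagnosis is recorded at enrolment, so an apical lesion present then is a known condition. If it grows, Table 4 classes the treatment as ineffective and the first rule in 14.2.1 says not an AE. The next paragraph of 14.2.1 says that worsening of a known condition is an AE. Both cannot be followed.

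**Step 4. What is kept.** Failure at 6 or 12 months counts as failure at 24 months (7.7.4). Symptoms and function are recorded at follow-up visits and enter Table 4. Extra consultations are compared in 7.7.6 whether or not an AE was recorded. What goes is the severity grade, seriousness, relatedness and expedited report.

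**Step 5. Scale.** Inputs from sections 7.2 and 7.3: 90% efficacy in both arms, 13-point margin, one-sided alpha 5%, power 80%, 66 per group raised to 80.
- The plan's figure first: n = [0.90 × 0.10 + 0.90 × 0.10] × (1.645 + 0.842)² / 0.13² = 65.85, so 66. Then 66 × 1.20 = 79.2, so 80. Both are reproduced.
- Expected failures = N × (1 − efficacy rate).

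| Efficacy | N = 80 | N = 66 |
|---|---|---|
| 90% | 80 × 0.10 = 8.0 | 66 × 0.10 = 6.6 |
| 77% (90% − 13 points, PA1704 only) | 80 × 0.23 = 18.4 | 66 × 0.23 = 15.2 |

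The share s of failures with symptoms or a serious outcome is not in the documents. The number of patients affected is at most s times these figures.

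**Step 6. Illustration under assumptions that are not in the documents.** Let a be the proportion with some other AE, the same in both arms and independent of failure. Put PA1704 at 77% and BioRoot RCS at 90%, and suppose that every symptomatic failure is excluded. The difference in patients with at least one AE that the exclusion hides is (1 − a) × s × 0.13.
- a = 5%, s = 100%: 0.95 × 1 × 0.13 = 12.4 points.
- a = 10%, s = 100%: 0.90 × 1 × 0.13 = 11.7 points (30.7% against 19.0%; 10% against 10% under the exclusion).
- a = 30%, s = 25%: 0.70 × 0.25 × 0.13 = 2.3 points.

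If the failure rates are equal, the hidden difference is zero when the rule is applied alike in both arms.

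**The case against.** The strongest reply is that 14.2.1 is a specific rule qualifying a general definition, written to keep the efficacy endpoint from being counted again as an AE. It has two limits that must both hold: the condition belongs to the dental pathology under study, and it is attributed to lack of effectiveness. Allergy, paraesthesia and instrument injury stay reportable. This stands as to scope, and leaving a bare efficacy outcome out of the AE listing is reasonable. It does not explain why a serious outcome should also be left out.

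A reader might infer that all failure-related harm disappears from the safety comparison. The documents do not support that, for the reasons in step 4. Nor is the consultation count in Table 3 a contradiction: visits and AEs are different measures, and the count is a partial safeguard. It triggers no SAE report, however.

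Other routes may be cited. The device-failure definition in 14.1 includes performance, and defects are recorded under 14.3. Section 14.2.6 covers urgent safety problems. Section 14.2.1 points to an eCRF guide that is not among the documents. None clearly restores the route: it is arguable whether a treatment failure is a device defect, and the urgent-safety definition is much narrower than the SAE definition. Referral of non-emergency failures to the trial coordinator concerns retreatment and exit, not AE status.

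A fair warning also stands. Without further wording, the intervention and chronic-illness criteria in 14.1 could turn ordinary retreatments or persisting lesions into SAEs.

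**Conclusion.** The concern holds in a limited form. Followed as written, the plan lets a failure-related event that is serious under 14.1 go without AE recording and without the 3-day report, on an unblinded judgement. It also gives two opposing instructions for growth of a lesion present at entry. The passages must be reconciled.

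The size is bounded, not known. About 8 of 80 failures per arm are expected at 90% efficacy, and about 18 of 80 on PA1704 at the margin (6.6 and 15.2 of 66). It is tempting to read these as unrecorded harms. They are not: Table 4 classes a symptom-free tooth with a new or larger lesion as ineffective, so some failures may involve no clinical harm. They are ceilings at those efficacy rates, provided that the exclusion is applied only to patients who count as failures on the primary endpoint.

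Nor do the documents show that the safety comparison is biased towards PA1704. That would need a higher failure rate on PA1704 or different use of the rule by arm. A true rate at the margin would usually show in the primary result, since the test is built to declare non-inferiority there only about 5% of the time. The documents also do not say which harms of PA1704 are most likely. The point rests on the missing exception for serious events, not on a forecast. The sample size is unaffected.

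**What to change.** Reconcile 14.1 and 14.2.1 by amendment:

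1. Limit the exclusion to the efficacy outcome itself, that is, the classification of the treatment as failed.
2. State that any event meeting a seriousness criterion in 14.1 is recorded and reported under 14.2.5, even when attributed to treatment failure.
3. State whether retreatment for failure alone falls under 14.1 b)iv or b)v, so that routine retreatments do not become SAEs by default.
4. State which of the two rules in 14.2.1 governs growth of an apical lesion present at entry.
5. Add an eCRF flag for events linked to treatment failure, and tabulate failure-linked symptomatic events by arm beside the AE comparison in 7.7.6.

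The separate table avoids having to count every symptomatic failure as an AE, which is more debatable because it partly counts the efficacy endpoint twice.

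The cost is amendment wording, one eCRF field and slightly higher event counts. Nothing changes in treatment, the primary analysis or the sample size.
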